5.3.2. Safety Data

Handling of missing information related to safety data, such as missing or partially missing date, will be in accordance with Pfizer reporting standards.

For derived variables in reactogenicity data, if any day of the 7-day e-diary is available, the "Day 1 - Day 7" data will be considered as nonmissing for analyses after each dose of Cohorts 2, 3 and 4. The proportion of subjects with missing reactogenicity data will also be summarized by each dose in Cohort 2, 3, and 4 for each vaccine group. The denominator will be the number of subjects who receive the scheduled vaccination.

6. ANALYSES AND SUMMARIES

- 6.1. Primary Endpoint(s)
- 6.1.1. Primary Immunogenicity Endpoints

6.1.1.1. Primary Analysis

Endpoints: Primary immunogenicity endpoints in Section 3.1

• Analysis time points:

Cohort 1: 1 month after the infant series.

Cohort 2, 3, 4: 1 month after the last dose of 13vPnC.

- Analysis population: Evaluable immunogenicity and all-available immunogenicity populations.
- Analysis methodology: See Section 5.2.2.
- Supporting objective: Primary Objective.

Reporting Results:

The number, GMC, and associated 95% CI at the above analysis time points will be presented for 13vPnC group in each Cohort; and GMR (compared with GMC of 13vPnC in Cohort 1), and associated 95% CI at the above analysis time points will be presented for Cohort 2, 3, 4.

Figures:

RCDCs will be presented graphically for each serotype-specific pneumococcal IgG antibody concentration of 13vPnC at the time point described as above in each Cohort. The RCDCs will plot all Cohorts on the same graph, distinguishable by symbol and/or line style choice.

6.1.2. Primary Safety Endpoints

6.1.2.1. Primary Analysis

Endpoints: Safety endpoints in Section 3.1.

• Analysis time points:

Endpoints for Local reactions and systemic events: 7 days after each vaccination in Cohort 2, 3 and 4.

Endpoints for AEs and SAEs: from the signing of the ICD to 1 month after the last vaccination (13vPnC or Hib vaccine) in Cohort 2, 3 and 4.

Endpoints for SAEs: from the signing of the ICD to 6 month after the last vaccination (13vPnC or Hib vaccine) in Cohort 2, 3 and 4.

Endpoint for newly diagnosed chronic medical conditions: from 1 month after the last vaccination (13vPnC or Hib vaccine) in Cohort 2, 3, and 4 to 6 months after the last study vaccination in Cohort 2, 3, and 4.

- Analysis population: Safety population.
- Analysis methodology: Descriptive.
- Supporting objective: Primary Objective.

Reporting Results:

The number, proportion, and the corresponding 95% CI will be presented for each vaccine group in Cohort 2, 3 and 4.

6.2. Secondary Endpoint(s)

6.2.1. Immunogenicity Endpoints in Section 3.2

Endpoint: The Serotype-specific OPA geometric mean titers (GMTs) for each of the pneumococcal serotypes measured in a subset of approximately 50 subjects per cohort.

• Analysis time points:

Cohort 1: 1 month after the infant series.

Cohort 2, 3, 4: 1 month after the last dose of 13vPnC.

- Analysis population: evaluable immunogenicity population and all-available immunogenicity population.
- Analysis methodology: See Section 5.2.

• Supporting objective: Secondary Objectives.

Reporting Results:

The number, GMT, and associated 95% CI at the above analysis time points will be presented for 13vPnC in each Cohort; and GMR (compared with GMT of 13vPnC in Cohort 1), and associated 95% CI at the above analysis time points will be presented for Cohort 2, 3, 4.

The numerator and denominator used for percentage, the percentage, and associated 95% CI will be presented for each vaccine group for infant series and toddler dose, and their percentage difference and corresponding CI will also be presented.

Figures:

RCDCs will be presented graphically for each serotype-specific pneumococcal OPA at 1 month after the last dose of 13vPnC in Cohort 2, 3, 4 and 1 month after the infant series in Cohort 1, and those RCDCs will be plotted on the same graph, distinguishable by symbol and/or line style choice.

Endpoint: Serotype-specific IgG GMCs in all subjects and OPA GMTs in approximately 50 subjects per cohort vaccinated with 13vPnC (Cohort 2, 3, 4) and approximately 25 subjects per cohort vaccinated with Hib (Cohort 2, 3, 4).

• Analysis time points:

Cohort 2: Visit 1, Visit 4.

Cohort 3: Visit 1, Visit 3.

Cohort 4: Visit 1, Visit 2.

- Analysis population: evaluable immunogenicity population and all-available immunogenicity population.
- Analysis methodology: See Section 5.2.2.
- o Supporting objective: Secondary Objectives.

Reporting Results:

The number, GMCs, and associated 95% CI at the above analysis time points will be presented for each vaccination for Cohort 2, 3, 4; and GMR (GMC comparison between 13vPnC and Hib vaccine) with associated 95% CI at the above analysis time points will be presented for Cohort 2, 3, 4.

The number, GMTs, and associated 95% CI at the above analysis time points will be presented for each vaccination for Cohort 2, 3, 4; and GMR (GMT comparison between 13vPnC and Hib vaccine) with associated 95% CI at the above analysis time points will be presented for Cohort 2, 3, 4.

The number, GMCs, and associated 95% CI at the above analysis time points will be presented for each vaccination in all Cohorts; and GMFR from Baseline (visit 1) with associated 95% CI will be presented for each vaccination in Cohort 2, 3, 4.

The number, GMTs, and associated 95% CI at the above analysis time points will be presented for each vaccination in all Cohorts; and GMFR from Baseline (visit 1) with associated 95% CI will be presented for each vaccination in Cohort 2, 3, 4.

The number, GMC, and associated 95% CI at visit 1 will be presented for 13vPnC group in each Cohort 2, 3, 4; and GMR at visit 1 (compared with GMC of 13vPnC in Cohort 1), and associated 95% CI will be presented for Cohort 2, 3, 4.

The number, GMT, and associated 95% CI at visit 1 will be presented for 13vPnC group in each Cohort 2, 3, 4; and GMR at visit 1 (compared with GMT of 13vPnC in Cohort 1), and associated 95% CI will be presented for Cohort 2, 3, 4.

The number, GMFRs, and associated 95% CI at post 13vPnC vaccination visit (4, 3, or 2) and the ratio of GMFRs(GMCs at post 13vPnC vaccination of Cohort 2, 3, 4 compared with GMCs at post infant series of Cohort 1) along with associated 95% CI will be presented.

The number, GMFRs, and associated 95% CI at post 13vPnC vaccination visit (4, 3, or 2) and the ratio of GMFRs(GMTs at post 13vPnC vaccination of Cohort 2, 3, 4 compared with GMTs at post infant series of Cohort 1) along with associated 95% CI will be presented.

Figures:

RCDCs will also be presented graphically for each serotype-specific pneumococcal IgG antibody concentration and OPA titer separately in each Cohort. The RCDCs will be plotted by vaccine group on the same graph for each Cohort, distinguishable by symbol and/or line style choice.

Endpoint: Serotype-specific IgG GMCs in all subjects and OPA GMTs in approximately 50 subjects in Cohort 1.

• Analysis time points:

Cohort 1: all time points in Cohort 1.

- Analysis population: evaluable immunogenicity population and all-available immunogenicity population.
- Analysis methodology: See Section 5.2.2.
- Supporting objective: Secondary Objectives.

Reporting Results:

The number, GMCs, and associated 95% CI at the above analysis time points; and GMFR from Baseline (visit 1) with associated 95% CI, will be presented in Cohort 1.

The number, GMTs, and associated 95% CI at the above analysis time points; and GMFR from Baseline (visit 1) with associated 95% CI, will be presented in Cohort 1.

Figures:

The antibody-response line plot of each serotype-specific GMCs and the associated 95% CI at time points after infant series of Cohort 1 will be presented.

The antibody-response line plot of each serotype-specific GMCs and the associated 95% CI at time points after infant series of Cohort 1 will be presented.

Endpoint: Proportion of subjects achieving a serotype-specific IgG concentration $\geq 0.35 \ \mu g/mL$ for each of the pneumococcal serotypes measured 1 month after the last dose in all subjects per cohort vaccinated with 13vPnC (Cohort 2, 3, 4) and all subjects per cohort vaccinated with Hib (Cohort 2, 3, 4) and 1 month after the infant series in all subjects vaccinated with 13vPnC in Cohort 1

• Analysis time points:

Cohort 1: 1 month after the infant series.

Cohort 2, 3, 4: 1 month after the last dose.

- Analysis population: evaluable immunogenicity population and all-available immunogenicity population.
- Analysis methodology: See Section 5.2.1.
- Supporting objective: Secondary Objectives.

Reporting Results:

The number, proportion, and the corresponding 95% CI will be presented for 13vPnC group in Cohort 1, 2, 3 and 4; and proportion difference with Cohort 1 along with associated 95% CI will be presented for Cohort 2, 3, 4.

PFIZER CONFIDENTIAL
Page 31

The number, proportion, and the corresponding 95% CI will be presented for each group in Cohort 2, 3 and 4; and proportion difference between 13vPnC and Hib vaccine, along with associated 95% CI will be presented for Cohort 2, 3, 4.

Endpoint: Proportion of subjects achieving a serotype-specific OPA titer \geq LLOQ for each of the pneumococcal serotypes measured 1 month after the last dose in approximately 50 subjects per cohort vaccinated with 13vPnC (Cohort 2, 3, 4) and approximately 25 subjects per cohort vaccinated with Hib (Cohort 2, 3, 4) and 1 month after the infant series in approximately 50 subjects in Cohort 1.

• Analysis time points:

Cohort 1: 1 month after the infant series.

Cohort 2, 3, 4: 1 month after the last dose.

- Analysis population: evaluable immunogenicity population and all-available immunogenicity population.
- Analysis methodology: See Section 5.2.1.
- Supporting objective: Secondary Objectives.

Reporting Results:

The number, proportion, and the corresponding 95% CI will be presented for 13vPnC group in Cohort 1, 2, 3 and 4; and proportion difference with Cohort 1 along with associated 95% CI will be presented for Cohort 2, 3, 4.

The number, proportion, and the corresponding 95% CI will be presented for each group in Cohort 2, 3 and 4; and proportion difference between 13vPnC and Hib vaccine, along with associated 95% CI will be presented for Cohort 2, 3, 4.

6.2.2. Safety Endpoints in Section 3.2.2

Endpoints: Safety endpoints in Section 3.2.2.

• Analysis time points:

Endpoint for the incidence of AEs from the signing of the ICD to 1 month after vaccination 3 in Cohort 1: from the signing of the ICD to 1 month after vaccination 3.

Endpoint for the incidence of newly diagnosed chronic medical conditions from 1 month after vaccination 3 to vaccination 4 in Cohort 1: from 1 month after vaccination 3 to vaccination 4.

Endpoint for the incidence of AEs from vaccination 4 to 1 month after vaccination 4 in Cohort 1: from vaccination 4 to 1 month after vaccination 4.

Endpoint for the incidence of newly diagnosed chronic medical conditions from 1 month after vaccination 4 to 6 months after vaccination 4 in Cohort 1: from 1 month after vaccination 4 to 6 months after vaccination 4.

Endpoint for incidence of SAEs from the signing of the ICD to 6 months after vaccination 4 in Cohort 1: from the signing of the ICD to 6 months after vaccination 4.

- Analysis population: Safety population.
- Analysis methodology: Descriptive.
- Supporting objective: Secondary Safety Objective.

Reporting Results:

The number, proportion, and the corresponding 95% CI will be presented.

6.3. Baseline and Other Summaries and Analyses

6.3.1. Study Conduct

6.3.1.1. Subject Disposition, Vaccination Administration, Blood Samples, and Screen Failures

The number and percentage of subjects who are randomized will be included in the subject disposition summary: subjects who withdraw during the vaccination phase, complete the vaccination phase, complete the study, and withdraw after the vaccination phase will be summarized. The reasons for withdrawal will also be tabulated. The reasons for withdrawal will be those specified in the database; no rewording/recoding will be done.

Subjects excluded from the evaluable immunogenicity population will also be summarized with reasons for exclusion.

The number and percentage of subjects randomized, vaccinated, and providing blood samples within the protocol-specified time frame, as well as before and after the specified time frame, will be tabulated for each vaccine group and total sample in each cohort.

A listing of noncompliant vaccine administration will be provided. The protocol deviations will also be listed. Subjects who do not receive the vaccine as randomized will be listed as well. A listing of subjects who withdrew because of AEs will be provided.

All assigned or randomized subjects will be used to generate these tables. All of the summary tables will be presented for each vaccine group and for the total in each cohort.

Subjects who sign the ICD but are screen failures will be also summarized separately for each vaccine group for each cohort.

6.3.1.2. Demographic, Medical History, and Baseline Characteristics

Descriptive summary reports for demographic characteristics will be provided for each vaccine group, separately for each cohort for the evaluable immunogenicity, all-available immunogenicity, and safety analysis populations.

If the evaluable and all-available immunogenicity populations differ by a small amount (eg, <5%), then demographics table will be produced for the evaluable immunogenicity population only.

Descriptive summary reports for medical history will be provided for each vaccine group for the safety population only.

6.3.1.3. E-Diary Completion

Variables defined in Section 3.5.1 will be summarized with descriptive statistics for each vaccine group and for the total after each dose for Cohort 2, 3 and 4. The safety population will be used to generate this table.

6.3.1.4. Analyses of Below LLOQ

A table summarizing the number of subjects with assay data below the LLOQ will be produced for each vaccine group separately for infant series and toddler dose. If the evaluable and all-available immunogenicity populations differ by a small amount (<5%), this table will be generated for the evaluable immunogenicity population only.

6.4. Safety Summaries and Analyses

All safety analyses will be summarized based on the safety population in accordance with Pfizer reporting standards. All safety summaries will be provided by vaccine group separately for each dose in infant series and toddler dose.

6.4.1. Adverse Events

It should be recognized that most studies are not designed to reliably demonstrate a causal relationship between the use of a pharmaceutical product and an AE or a group of AEs. Except for select events in unique situations, studies do not employ formal adjudication procedures for the purpose of event classification.

For tier 1 and tier 2 events, the proportion of AEs observed in each vaccine group will be presented along with the point estimates and associated 95% CIs of the risk difference (the difference of incidence rates) between 13vPnC and Hib vaccine in Cohort 2, 3, 4.

For tier 1 events, 95% CIs will be calculated using the exact methods proposed by Chan and Zhang described in Section 5.2.1.

For tier 2 events, 95% CIs will be calculated using the Miettinen and Nurminen method described in Section 5.2.1.

For tier 1 events, p-values from Chan and Zhang's method will be calculated and included in the presentations. AEs will be arranged in the output sorted in descending order of point estimates of the risk difference (the difference of incidence rates) within system organ class.

6.4.2. Reactogenicity Data

The derived endpoints (Section 3.4.2) for each local reaction, systemic event, and use of antipyretic/pain medication to prevent or treat symptoms will be summarized.

The presence and maximum severity of the local reaction and systemic event at "any day (Day 1 - Day 7)" for each vaccination (13vPnC or Hib) following each dose in Cohort 2, 3, 4 will be summarized by proportions of subjects with the associated 95% Clopper-Pearson CIs.

The presence of each local reaction and systemic event on any day (Day 1-7), any local reaction on any day (Day 1-7), maximum severity of each local reaction and systemic event on any day (Day 1-7) following any vaccination in Cohort 2, 3, 4 will also be summarized by proportions of subjects with associated Clopper-Pearson CIs. For local reactions, systemic events, and use of antipyretic/pain medication to prevent or treat symptoms, descriptive summary statistics of the maximum duration of the event will be provided.

For the onset of local reactions, systemic events, and use of antipyretic/pain medication to prevent or treat symptoms, descriptive summary statistics of the onset day will be provided.

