Prevenar 13, the 13-valent pneumococcal conjugate vaccine (13vPnC) was approved in China in October 2016 for the prevention of invasive pneumococcal disease in infants 6 weeks to 15 months of age. The approved regimen only allows vaccination with Prevenar 13 at 2, 4, 6 months for the primary series and the toddler or booster dose at 12 to 15 months of age. Prevenar, the 7-valent vaccine that was used as a comparator in the Phase 3 study in China had been approved through 5 years of age (up to the 6th birthday). The safety and immunogenicity of 7vPnC in children 7 months up to 5 years of age had been assessed in a post-licensure study (Study number B1841008).

The Center for Drug Evaluation (CDE) requested that safety and immunogenicity of Prevenar 13 be assessed in children 7 months to 5 years of age (before the 6th birthday). CDE also requested that Pfizer provide antibody persistence data through 5 years of age in children vaccinated as infants. This study is designed to support licensure of 13vPnC from

7 months through 5 years of age and to address both of these post licensure commitments from the CDE.

This study includes 4 separate cohorts broken down by age. Cohorts 2, 3 and 4 range in age from 7 months to 5 years of age (Cohort 2 - 7 months to <12 months of age; Cohort 3 - ≥ 1 year to <2 years; Cohort 4 - ≥ 2 years to <6 years of age). These three cohorts are of primary interest in obtaining licensure in the 7 months to 5 year age range and addressing the CDE request to obtain safety and immunogenicity data in this age group. Immune responses before and after the last vaccination in each of these age groups will be measured and used as a surrogate of efficacy. Cohort 1 will include infants 6 weeks to 2 months of age that will be vaccinated with 13vPnC according to the currently licensed infant schedule (2, 4, 6 and 12 to 15 months). Post vaccination serotype specific serum anticapsular IgG responses in Cohorts 2, 3, and 4 will be compared to the post infant series responses in Cohort 1 as a bridge to efficacy. Cohorts 2, 3, and 4 will also include a control group vaccinated with *Haemophilus influenzae* type b (Hib) vaccine. The Hib vaccinated infants and children will serve as controls for assessment of the safety and immunogenicity of Cohorts 2, 3, and 4.

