7. ASSESSMENTS

Every effort should be made to ensure that the protocol-required tests and procedures are completed as described. However, it is anticipated that from time to time there may be circumstances outside of the control of the investigator that may make it unfeasible to perform the test. In these cases the investigator will take all steps necessary to ensure the safety and well-being of the subject. When a protocol-required test cannot be performed, the investigator will document the reason for this and any corrective and preventive actions that he or she has taken to ensure that normal processes are adhered to as soon as possible. The study team will be informed of these incidents in a timely manner.

For samples being collected and shipped, detailed collection, processing, storage, and shipment instructions and contact information will be provided to the investigator site prior to initiation of the study.

A complete medical history and physical examination will be performed on all subjects before randomization. The CRFs will capture the medical history and physical examination done at visit 1 to establish a baseline.

Safety parameters will be assessed as described in the Schedule of Activities Procedures section, Adverse Events section. In addition use of antipyretic medication, local reaction and systemic event data will be collected in an electronic diary for 7 days after each dose of investigational product in Cohorts 2, 3 and 4.

7.1. Electronic Diary – Cohorts 2, 3, and 4

The caregiver will be issued an e-diary, and will be asked to monitor and record the subject's local reactions and systemic events (including the use of antipyretic medication), for 7 days after each investigational product (13vPnC or Hib vaccine) vaccination. The e-diary allows recording of these assessments only within a fixed time window, thus providing the accurate representation of the subject's experience at that time. Use of antipyretic medication, local reactions and systemic events reported on the e-diary will be transferred electronically to the e-diary vendor (a trusted third party), where they will be available for review by investigators at all times via an Internet-based portal. At intervals agreed upon between the vendor and Pfizer, these data will be transferred electronically into Pfizer's database for analysis and reporting. These data do not need to be reported by the investigator on the CRF.

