2.2. Study Design

- This is a phase 3 randomized, open-label study to evaluate the safety, tolerability, and immunogenicity of 13vPnC in infants and young children who are naïve to pneumococcal vaccination.
- Subjects will be stratified into 4 cohorts defined by their age pleat consent:
 - Cohort 1: Subjects 6 weeks (42 days) to 2 months (56 days) of age;
 - Cohort 2: Subjects 7 months (210 days) to <12 months (<365 days) of age;
 - Cohort 3: Subjects ≥ 1 year to ≤ 2 years of age;
 - Cohort 4: Subjects ≥ 2 years to <6 years of age.

- Subjects in Cohort 1 will all receive 13vPnC at 2, 4, 6 and 12 to 15 months of age. See Table 2 below.
- Subjects in Cohorts 2, 3, and 4 will be randomized into 2 groups in a 2:1 ratio to receive 13vPnC or comparator (Hib vaccine) according to age-appropriate schedules. See Table 2 below.

		Age at first vaccination	Age at second vaccination	Age at third vaccination	Age at fourth vaccination
Cohort 1	13vPnC	42 to 56 Days of	42 to 70 Days After	42 to 70 Days	365 to 455
		Age	Visit 1	After Visit 2	Days of Age
Cohort 2	13vPnC or	7 to <12 Months	At Least 28 Days	365 Days to <450 Days	
	Hib	of Age	After Visit 1	of Age and at Least 56	
		_		Days After Visit 2 ^a	
Cohort 3	13vPnC or	≥ 1 to <2 Years	At Least 56 Days		
	Hib	of Age	After Visit 1 ^b		
Cohort 4	13vPnC or	≥ 2 to <6 Years			
	Hib	of Age			

Table 2. Age at Vaccination

a. Subjects in Cohort 2 randomized to Hib vaccine will not receive a vaccination at Visit 3. These subjects may receive a third dose of Hib vaccine according to local practice or national recommendations, at the discretion of the investigator.

b. Subjects in Cohort 3 randomized to Hib vaccine will not receive a vaccination at Visit 2.

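### The any-vaccination reactogenicity summary in SAP 6.4.2 covers unequal diary time (13vPnC v Hib: 21 v 14 days in Cohort 2, 14 v 7 in Cohort 3) and is not a like-for-like comparison

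*SAP*

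**What the plan says.** SAP 6.4.2 plans two kinds of reactogenicity summary. The first is per dose: presence and maximum severity "for each vaccination (13vPnC or Hib) following each dose in Cohort 2, 3, 4 will be summarized by proportions of subjects". The second pools over doses: presence of each reaction or event, any local reaction, and "maximum severity of each local reaction and systemic event on any day (Day 1-7) following any vaccination in Cohort 2, 3, 4", again as proportions with Clopper-Pearson intervals. SAP 6.4 sets the layout: "All safety summaries will be provided by vaccine group separately for each dose in infant series and toddler dose".

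The diary runs "for 7 days after each investigational product (13vPnC or Hib vaccine) vaccination" (Protocol 7.1). The arms do not receive the same number of study doses. SAP 2.2 states "Subjects in Cohort 2 randomized to Hib vaccine will not receive a vaccination at Visit 3" and "Subjects in Cohort 3 randomized to Hib vaccine will not receive a vaccination at Visit 2". The flowcharts (Protocol Tables 2 and 3, footnotes b and a) limit the corresponding diary week to 13vPnC recipients. A further Hib dose in Cohort 2 is permitted but falls outside the study (Protocol 6.2.3), so it opens no diary period.

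Protocol 1.2 gives the role of the comparator: "The Hib vaccinated infants and children will serve as controls for assessment of the safety and immunogenicity of Cohorts 2, 3, and 4".

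**The concern.** A solicited reaction can be counted only while a diary is open. The pooled row asks whether a child had the reaction in any diary period, and children in the 13vPnC arm have one more period than Hib children in Cohorts 2 and 3. Some diary items, such as irritability, reduced appetite and raised temperature, also occur without a vaccine, so an extra week can add events whatever was injected. Maximum severity over more periods is affected in the same way.

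Hib is the randomised safety control, so readers will compare the two columns. In the pooled row they cannot separate a vaccine effect from an additional dose and week of observation. Neither document restricts this row to shared doses, allows for the number of doses, or adds a caution.

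**Working it through.** **Diary time** (study doses × 7 days):

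| Cohort | 13vPnC | Hib |
|---|---|---|
| 2 | 3 × 7 = 21 | 2 × 7 = 14 |
| 3 | 2 × 7 = 14 | 1 × 7 = 7 |
| 4 | 1 × 7 = 7 | 1 × 7 = 7 |

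These counts need no assumption.

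**Direction.** If each dose carries the same risk p in both arms, the chance of a reaction after at least one of k doses cannot fall as k rises. It stays level only if an extra dose never adds a new reactor.

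**Size.** The documents give no reaction rate, so p and the within-child correlation ρ are assumptions. Let q = 1 − p.

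- Independent doses: P(any of k) = 1 − q^k.
- Correlated doses (beta-binomial): P(none of 2) = q × [q(1 − ρ) + ρ]. P(none of 3) is that value × [q(1 − ρ) + 2ρ] / (1 + ρ).

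With p = 0.20:

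- ρ = 0: one dose 0.200; two doses 1 − 0.8² = 0.360; three doses 1 − 0.8³ = 0.488.
- ρ = 0.5: two doses 1 − 0.8 × 0.9 = 0.280; three doses 1 − 0.72 × 1.4/1.5 = 0.328.
- ρ = 0.9: two doses 1 − 0.8 × 0.98 = 0.216; three doses 1 − 0.784 × 1.88/1.9 = 0.224.

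| ρ | Cohort 3 (2 v 1 doses) | Gap, points | Cohort 2 (3 v 2 doses) | Gap, points |
|---|---|---|---|---|
| 0 | 36.0% v 20.0% | 16.0 | 48.8% v 36.0% | 12.8 |
| 0.5 | 28.0% v 20.0% | 8.0 | 32.8% v 28.0% | 4.8 |
| 0.9 | 21.6% v 20.0% | 1.6 | 22.4% v 21.6% | 0.8 |
| 1 | 20.0% v 20.0% | 0 | 20.0% v 20.0% | 0 |

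For independent doses and p from 5% to 40%, the Cohort 3 pair runs from 9.8% v 5.0% to 64.0% v 40.0%, and the Cohort 2 pair from 14.3% v 9.8% to 78.4% v 64.0%.

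**Illustration only.** Suppose a reader formed a 95% Wald interval for the difference at the planned 118:59 split (Protocol Table 15), with p = 0.20. By exact enumeration it would exclude zero, in Cohort 3 / Cohort 2, about 65% / 39% of the time at ρ = 0, 25% / 11% at ρ = 0.5 and 7% / 6% at ρ = 0.9. A normal-approximation power formula gives 59% / 36% at ρ = 0. The SAP plans no such interval.

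**After matching.** Over Doses 1-2 in Cohort 2 and Dose 1 in Cohort 3, diary time is 14 v 14 and 7 v 7 days. The expected difference at equal per-dose risk is then zero for every p and ρ.

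**The case against.** The strongest reply is that the equal-exposure comparison is already planned. The primary reactogenicity endpoint (SAP 3.1.2) is defined after each vaccination, the per-dose tables follow it, and the pooled row is an addition. This stands.

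Nor does the SAP set up a contrast between arms here. Reactogenicity gets a separate interval for each group; risk differences are planned only for tier 1 and tier 2 adverse events (SAP 5.2.1, 6.4.1), and SAP 5.1 disclaims formal hypotheses. This also stands, and the exclusion percentages above are illustrative for that reason.

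The all-dose row can also be read as a child's risk over the assigned regimen. For that question it is correct, since more doses do bring more reactions. What remains is that Hib in the neighbouring column is not a like-for-like control for it, and nothing on the row says so.

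A reader might infer that the primary safety comparison is biased, or that a false difference would appear about two times in three. The documents support neither. The primary tables are per dose, and the high figure requires a 20% risk, independent doses in the same child and an interval that nobody has planned. The distortion also makes 13vPnC look worse, so at equal per-dose risk it does not create false reassurance.

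**Conclusion.** The point holds as a limited matter of presentation and comparability. In Cohorts 2 and 3 the pooled row compares the arms over diary time in ratios of 1.5 (21/14) and 2.0 (14/7). At equal per-dose risk this favours Hib unless an extra dose never adds a reactor. The ratios are exact. The size of the gap is not: at an assumed 20% per dose it lies between 16 and 1.6 points in Cohort 3, and between 12.8 and 0.8 points in Cohort 2, for correlations from 0 to 0.9. The all-dose 13vPnC figure is valid as a description of the full schedule. Cohort 4 and all per-dose tables are unaffected. The point covers presence, any local reaction and maximum severity; SAP 6.4.2 does not say that duration is pooled over doses.

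**What to change.** In SAP 6.4.2, state that the side-by-side 13vPnC and Hib any-vaccination comparison is made over the doses that both arms receive.

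- **Cohort 2:** add a Doses 1-2 row.
- **Cohorts 3 and 4:** use the Dose 1 row already planned.
- **All cohorts:** keep the all-dose row as a regimen-level description, labelled with the number of doses and diary periods in each arm.

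Add to the pooled row and do not redefine it. SAP 2 says that the analyses had already been performed for the primary report and will be repeated with the 280 additional subjects, and keeping the row lets the supplemental tables be read against the earlier ones. The larger sample would narrow the intervals but leave the imbalance in place. The change follows from the dosing schedule and not from results.

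The cost is SAP wording, one extra row for Cohort 2 and a label; no new data are needed. The downside is that the matched row omits the last 13vPnC dose, which stays visible in the per-dose and all-dose rows.
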